Upon arrival in the PACU, all patients will be monitored according to standard post-anesthesia protocols for a period of at least 2 hours. The PACU nurse that is blinded to treatment group will assess and record baseline vital signs including HR, BP, RR, SpO2, and VRS score. Modified Aldrete score including presence of nausea/vomiting, sedation level or evidence of dysphoria will be recorded at 15 minute intervals. SpO2 will be monitored continuously with documentation of oxygen flow required to maintain oxygen saturation of at least 94%. As per PACU protocol, initially patients will receive oxygen 40% by open face mask, with weaning to NC or RA, maintaining SpO2 > 94%. Desaturation episodes will be scored automatically by pulse oximetry analysis software (Nellcor, NPB-290). Data evaluated will include: comparison of patient demographics, time to first analgesic, number of analgesic demands, amount of analgesic consumed in the OR and PACU, frequency of side effects, and ODI (oxygen desaturation index). ODI is defined as the number of desaturations (lower than 4% from baseline) per hour of recording, which correlates with PSGdetermined apnea/hypopnea index and can be used as an indicator of postoperative apneic episodes <Ahmad S, Anesthesia and Analgesia 2008>}. Time to first analgesia request will be recorded and pain (VRS >/= 4) will be treated with intravenous morphine 2mg. This will be repeated at 5 minutes intervals until pain score improves or patient has untoward side

effects, at which time the PACU physician should be immediately called to the patient's bedside. Further monitoring for of patients in PACU or on the floor may be indicated in some patients according to the discretion of the attending anesthesiologist and surgeon; however it is not mandatory for this study. According to Terris et al., "Significant complications [of OSA] generally emerge within 2 hours after surgery. Therefore a decision regarding the level of postoperative monitoring needed may be made with confidence during the period of time that the patient is in the recovery room" <Terris DJ, Laryngoscope 1998>.

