# 11.0 STATISTICAL CONSIDERATIONS

Statistical analysis with *a priori* power analysis was performed to determine the number of patients per group sufficient to detect a decrease of >30% in postoperative opioid requirements on the basis of the results of Kararmaz et al., Anesthesia and Analgesia 2003. With a power of 80% and a type 1 error of 5%, it was estimated that 32 patients will be required per group. We will plan to enroll 65 patients total to account for unanticipated subject dropout. Mann-Whitney U-test will be used to compare VRS, modified Aldrete, and patient satisfaction scores. Student's t-test will be used to compare BMI, time to first analgesic, number of analgesic demands, amount of analgesic consumption and ODI. The X2 test will be used to compare frequency of side effects, race and sex distribution. The resulting values will be expressed as mean +/- SD or median and range with P< 0.05 considered statistically significant.

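### The plan analyses time to first analgesic but says it will record time to first request, and score-triggered PACU morphine can be given before any request

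*Combined protocol and SAP*

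**What the plan says.** Section 8.0 lists among the data to be evaluated "time to first analgesic, number of analgesic demands, amount of analgesic consumed in the OR and PACU". Sections 5.0 and 11.0 send these variables to one test: "Student's t-test will be used to compare BMI, time to first analgesic, number of analgesic demands, amount of analgesic consumption and ODI".

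For PACU data collection, section 8.0 states: "The PACU nurse that is blinded to treatment group will assess and record baseline vital signs including HR, BP, RR, SpO2, and VRS score". This happens on arrival. No schedule for later pain scores is given; the 15-minute interval belongs to the Aldrete assessment. On analgesia the section says "Time to first analgesia request will be recorded and pain (VRS >/= 4) will be treated with intravenous morphine 2mg", and on further doses "This will be repeated at 5 minutes intervals until pain score improves or patient has untoward side" effects, when the PACU physician is called.

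The text does not give a time origin, a rule for a patient dosed before asking, a rule for a patient who never asks or is never dosed, or a definition or data source for a demand. No patient-controlled device is described for the PACU.

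**The concern.** Request and dose are separate events under section 8.0. The endpoint's name points to the dose, and the recording instruction points to the request. Both the first and the repeat doses can be given on the score alone, so the two times can differ for the same patient.

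The difference is unlikely to be random. Patients most exposed to being dosed unasked are those with a high score on arrival. Section 4.0 hypothesises lower pain scores with ketamine, so the trial itself expects more of them in the saline arm. If request time is what gets analysed, saline times are pushed later than ketamine times, which works against the effect the trial is looking for. If the request field is instead left blank, the t-test drops the patients in most pain, and the comparison is no longer between the groups as randomised.

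**Working it through.** **The plan's own figure.** The plan states "With a power of 80% and a type 1 error of 5%, it was estimated that 32 patients will be required per group", for a number "sufficient to detect a decrease of >30% in postoperative opioid requirements". No mean or SD is given, so 32 cannot be reproduced from the documents. Solving backwards (two-sided, normal approximation): d = (1.96 + 0.84) × √(2/32) = 0.70, and a 30% decrease then needs a coefficient of variation of 0.30/0.70 = 0.43. That figure concerns opioid amount, so nothing below alters it.

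**Applying the text to three invented patients**

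| Patient | Course | First request | First dose | Requests | Doses |
|---|---|---|---|---|---|
| A | VRS 8 on arrival; dosed at 0, 5, 10, 15 min; first asks at 60 min and is dosed again | 60 min | 0 min | 1 | 5 |
| B | VRS 2 on arrival; asks at 30 min with VRS 5; one dose | 30 min | 30 min | 1 | 1 |
| C | Asks at 20 min with VRS 3; not treated | 20 min | none | 1 | 0 |

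By request, A needs analgesia later than B. By dose, A needs it first. Two coders following section 8.0 could enter 0 or 60 minutes for A.

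**How large the loss could be.** Every input here is an assumption; the documents give none of them.

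- p: proportion with VRS of 4 or more on arrival, 60% saline and 40% ketamine, dosed at 2 min.
- Other patients ask and are dosed together, at exponential times with mean 45 min (saline) or 60 min (ketamine), capped at 120 min.
- s: share of arrival-pain patients who ask at once. The rest first ask a mean of 60 min after that dose.

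The mean of an exponential time with mean m, capped at c, is m(1 − e^(−c/m)). This gives 41.9 min (m = 45) and 51.9 min (m = 60) at c = 120. The mean extra delay for those who do not ask at once is D = 60(1 − e^(−118/60)) = 51.6 min.

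- By first dose: saline 0.6 × 2 + 0.4 × 41.9 = 17.9; ketamine 0.4 × 2 + 0.6 × 51.9 = 31.9; difference 14.0 min.
- By first request: difference = 14.0 − (p saline − p ketamine)(1 − s)D = 14.0 − 0.2 × (1 − s) × 51.6.

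| s | Difference by request (min) | Share kept |
|---|---|---|
| 0 | 3.7 | 26% |
| 0.5 | 8.8 | 63% |
| 0.8 | 11.9 | 85% |
| 0.9 | 12.9 | 93% |

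Simulation agrees to within Monte Carlo error (26 to 27% kept at s = 0). With 32 per arm it gives t-test power of 35% by dose and about 7% by request at s = 0.

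The loss term contains the difference in arrival-pain rates, so it vanishes when they are equal: at 50% in both arms the difference is 5.0 min either way. Varying the rates from 80/60% to 40/20%, the later-request mean from 30 to 90 min, and s between 0 and 0.5, the share kept runs from −10% to 82%. The share kept does not depend on the number of patients; the power figures do.

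**A second model, including blanks.** Here arrival-pain patients are dosed within 0 to 5 min, and the others at 5 min plus an exponential time of mean 30 (control) or 45 min (ketamine). Arrival-pain patients either have no request time or ask 15 to 60 min after the dose. Power with 32 per arm:

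| Arrival pain, control/ketamine | First dose | Request blank | Request late |
|---|---|---|---|
| 20/10% | 42% | 27% | 27% |
| 40/20% | 52% | 21% | 24% |
| 60/30% | 64% | 13% | 16% |
| 60/60% | 10% | 13% | 12% |

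Power is lost when arrival pain differs between arms, and not when it is equal.

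**The case against.** The strongest reply is that this is loose wording, not a biased measurement rule. The variable carries the name of the analgesic, not the request, in all three sections, and dose times should be in the medication record, so an analyst could simply use the first dose. Section 8.0 also puts request and treatment in one sentence. It can be read as: the patient complains, the score is checked, morphine follows at 4 or more. With no schedule for scores after arrival, a request is a plausible prompt for scoring, and a high arrival score might itself be logged as a request. Patient A is an extreme case, and the simulated loss depends on inputs chosen by the reviewer.

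Much of this stands. A reader might infer three stronger things that the documents do not support:

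- That patients in most pain will get late or blank times. The text permits dosing before a request; it does not say that this will happen, or how often.
- That demands will be undercounted. A demand could be a request, a score of 4 or more, or a dose. Patient A's one request against five doses shows a possibility only.
- That the trial's main result is compromised. The sample size and the opioid-amount comparison do not use request times.

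What does not stand is the suggestion that nothing needs changing. The only recording instruction names the request, nothing covers a patient dosed before asking, and the ambiguity bears most on patients in pain on arrival.

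**Conclusion.** The point holds as a mismatch between what is analysed (first analgesic), what is to be recorded (first request) and what triggers treatment (the score). If request time is used, and arrival-pain patients are dosed before asking and are commoner on saline, a real ketamine delay is biased towards zero. The size is unknown: under the 60/40% assumption the share kept runs from about a quarter to over 90%, depending on how many ask at once. Reversal appears only at the far end of the assumed range. With equal arrival pain there is no loss. For the number of demands, the finding is only that the term is undefined. This is worth correcting, but it does not affect the opioid-amount comparison or the sample size.

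**What to change.** - In section 8.0, define time to first analgesic as the time from PACU arrival to the first PACU morphine dose given, taken from the medication record.
- Censor patients with no PACU dose at two hours, the minimum PACU observation that section 8.0 sets for everyone. In sections 5.0 and 11.0, move this variable from the t-test to a log-rank test, so that undosed patients contribute instead of being left blank.
- Keep request time, if wanted, as a separate descriptive field.
- Define the number of demands as the number of PACU morphine doses given. With fixed 2 mg doses this equals the PACU morphine amount in mg divided by 2, so report it descriptively and do not test it as a separate outcome.

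The treatment rule is unchanged. The cost is wording in sections 5.0, 8.0 and 11.0 and one field on the PACU form, assuming dose times are already charted. The small downside is that an unmet request, as in patient C, no longer counts as an event. The change is best made before enrolment under the re-opened protocol (Human Subjects Protocol, item 23), because requests that were never logged separately cannot be recovered later.

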When patients are deemed suitable for discharge from the PACU, patients will be transferred to the floor where they will receive standard hospital care and monitoring including routine vital signs continuous pulse oximetry. At 24 hrs post-op, patient vital signs, VRS, and morphine usage will be assessed along with patient satisfaction related to overall anesthesia care according to a 5-point scale (1= very unsatisfied, 2=unsatisfied, 3=equivocal, 4=satisfied, 5=very satisfied).

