#### 15. Participants (Screening and Selection)

- a. How many participants are to be enrolled at UAB?  $\underline{150}$  If multi-center study, total number at all centers:  $\underline{N/A}$
- **b.** Describe the characteristics of anticipated or planned participants.

Sex: Male or Female

Race/Ethnicity: All representative of patients undergoing general ENT or Orthopedic surgery; Expand the patient population to include all patients undergoing surgery requiring to general anesthesia due to the limited amount of patients that are able to be recruited.

Age: 18-100

Classification of 1-3 and who are morbidly obese patients with obstructive sleep apnea scheduled general ENT or Orthopedic surgery. ASA Classification of 1 = A normal healthy patient, ASA Classification of 2 = A patient with mild systemic disease (examples: current smoker, social alcohol drinker), ASA Classification of 3 = A patient with significant systemic disease (examples: Poorly controlled diabetes or hypertension), and ASA Classification of 4 = A patient with severe systemic disease that is a constant threat to life (examples: MI, CVA, TIA, or CAD/stents, ongoing

cardiac ischemia or severe valve dysfunction, severe reduction of ejection fraction, sepsis, DIC, ARD or ESRD not undergoing regularly scheduled dialysis).

Note. If data from prior studies indicate differences between the genders or among racial/ethnic groups in the proposed research or if there are no data to support or to negate such differences, Phase 3 clinical trials will be required to include sufficient and appropriate entry of gender and racial/ethnic subgroups so that trends detected in the affected subgroups can be analyzed. If ethnic, racial, and gender estimates are not included in the protocol, a clear rationale must be provided for exclusion of this information. If prior evidence indicates that the results will not show gender or racial differences, researchers are not required to use gender or race/ethnicity as selection criteria for study participants. They are, however, encouraged to include these groups. See Section II. Policy of the NIH POLICY AND GUIDELINES ON THE INCLUSION OF WOMEN AND MINORITIES AS SUBJECTS IN CLINICAL RESEARCH – Amended, October, 2001) for further details.

C. From what population(s) will the participants be derived?
The study population will be derived from those patients who are morbidly obese scheduled to undergo general ENT and orthopedic surgery.

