Describe your ability to obtain access to the proposed population that will allow recruitment of the necessary number of participants:
All patients scheduled for the above surgical procedure will be seen preoperatively in the PAC at TKC and Highlands. The opportunity to participate will be offered at such time.

Describe the inclusion/exclusion criteria:

Inclusion criteria: aged 19-100, scheduled to undergo general ENT or Orthopedic Surgery.

Patients should have a diagnosis of obstructive sleep apnea as confirmed by sleep study or deemed high risked for obstructive sleep apnea by clinical predictors (greaterthan 4 clinical predictors of obstructive sleep apnea as described by STOP BANG).

Exclusion criteria: positive pregnancy test, ASA> III, history of alcohol or narcotic abuse in last 90 days, significant cardiovascular or respiratory disease (baseline oxygen saturation below 92%), significant psychiatric or neurologic disease, history of significant hepatic or renal disease (baseline creatinine>1.5), history of allergy or contraindication to anesthetic agents or ketamine including patients with increased ICP, increased IOP, severe arrhythmias, history of delirium, hallucinations, or psychosis, or history of uncontrolled seizures, or potential risk for malignant hyperthermia (family history), history of difficult intubation that would preclude standard induction of anesthesia, prisoners, persons who are mentally impaired, and non-English speakers.

- **d.** If participants will comprise more than one group or stratification, describe each group (e.g., treatment/intervention, placebo, controls, sham treatment) **and** provide the number of participants anticipated in each group.

  Participants will be randomly assigned to either the low-dose Ketamine infusion group or the normal saline infusion group. The two groups will comprise the study population, n=150.
- e. Indicate which, if any, of the special populations listed below will be involved in the protocol. Include the Special Populations Review Form (SPRF) if indicated.

  □ Pregnant Women: Attach SPRF—Pregnant Women, Fetuses, Neonates/Nonviable Neonates

□ Fetuses: Attach SPRF—Pregnant Women, Fetuses, Neonates/Nonviable
Neonates
□ Neonates/Nonviable Neonates: SPRF—Pregnant Women , Fetuses ,
Neonates/Nonviable Neonates
□ Prisoners: Attach SPRF—Prisoners
☐ Minors (<18 years old): Attach SPRF—Minors
⋈ Employees or students at institution where research conducted

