# 16. Protocol Procedures, Methods, and Duration of the Study—in nontechnical language

- Participants in this study will be randomized to two groups: One group will receive an intravenous (IV) dose of ketamine during the surgery. The other group will receive a normal saline placebo IV (control group). For the patients that are randomized to the ketamine group, the PI will submit an order for the ketamine to the research pharmacist. The pharmacist will determine the dosing of ketamine based on a standard calculation and prepare the syringe that will be used to dispense the ketamine. For both groups, the IV infusion will be discontinued at the conclusion of the surgery. Participants will receive standard anesthetic drugs and appropriate pain medication to control their postoperative pain in keeping with the current practice. We will compare recovery data including vital signs and pain scores as well as potential side effects of controlled versus study group. Approximately 24 hours after surgery, a patient assessment form will be completed ("24 Hr Post-Operative Data Collection Form") by the PI or research study team.
- b. What is the probable length of time required for the entire study (i.e., recruitment through data analysis to study closure)?
  Approximately two years
- Participants will be involved during surgery, during their recovery in the PACU, and at one time point approximately 24 hours postoperatively (to complete the Post-Operative Patient Satisfaction Assessment Form).
- d. If different phases are involved, what is the duration of each phase in which the participants will be involved? If no phases are involved, enter "not applicable." Not applicable
- **e.** List the procedures, the length of time each will take, and the frequency of repetition, and indicate whether each is done solely for research or would already be performed for treatment or diagnostic purposes (routine care) for the population. *Insert additional table rows as needed.*

Procedure	Length of Time	Frequency of	Doscorrah (Dos)
rioccarc			Research (Res) -
	Required of	Repetition	OR- Routine Care
	Participants		
Pregnancy testing for women of	<5 minutes	once	□Res ⊠Routine
childbearing potential			
Weight measurement	<5 minutes	once	□Res ⊠Routine
Normal Saline or Ketamine infusion	<three hours<="" td="">once	⊠Res □Routine	</three>	once	⊠Res □Routine
Monitoring and measurement of	From onset of	Continuously	□Res ⊠Routine

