#### Common adverse reactions include:

Hypersalivation, anorexia, nausea/vomiting, hypertension, hypotension, tachycardia, bradycardia, diplopia, nystagmus, fasciculations, depressed reflexes, and hallucinations. Common side effects are typically reversible with cessation of the infusion.

- **b.** Estimate the frequency, severity, and reversibility of each risk listed. Please see item 18.a.
- **c.** Is this a therapeutic study or intervention?

⊠Yes □No

If Yes, complete the following items:

- i. Describe the standard of care in the setting where the research will be conducted: Balanced general anesthetic with postoperative intravenous opioids.
- ii. Describe any other alternative treatments or interventions: N/A
- iii. Describe any withholding of, delay in, or washout period for standard of care or alternative treatment that participants may be currently using: None
- d. Do you foresee that participants might need additional medical or psychological resources as a result of the research procedures/interventions? ☐Yes ☒No If Yes, describe the provisions that have been made to make these resources available.

If No, provide justification for performing the research:\_\_\_\_

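### The 24-hour opioid item counts morphine only, while floor analgesia is not restricted to morphine, so as written any other opioid given on the floor would not be counted

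*Combined protocol and SAP*

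**What the plan says.** Section 8.0 fixes the rescue opioid in the PACU: "pain (VRS >/= 4) will be treated with intravenous morphine 2mg", repeated every 5 minutes. After PACU discharge, patients are "transferred to the floor where they will receive standard hospital care and monitoring", and no floor opioid is named. The next-day assessment is then stated: "At 24 hrs post-op, patient vital signs, VRS, and morphine usage will be assessed". No start time, route or conversion to a common opioid unit is given.

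The re-submitted Human Subjects Protocol form is no narrower. Item 16 provides for "appropriate pain medication to control their postoperative pain in keeping with the current practice". Item 18.c gives the local standard of care as "Balanced general anesthetic with postoperative intravenous opioids", which is a drug class. Section 9.0 (Concomitant Therapies) sets no rule. Item 15 widens the surgical population ("Expand the patient population to include all patients undergoing surgery") and sets the size: "The two groups will comprise the study population, n=150".

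Section 11.0 sizes the trial on a number of patients "sufficient to detect a decrease of >30% in postoperative opioid requirements", without saying over what period. Its t-test list includes the amount of analgesic consumed but names no drug, window or conversion. The list of data to be evaluated in section 8.0 places the analgesic amount in the operating room and PACU.

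**The concern.** The trial's rationale is that patients with sleep apnea are sensitive to the respiratory effects of opioids as a class. Section 2.0 asks whether the opioid-sparing effect of ketamine persists in them. The 24-hour assessment is the only opioid measure described that reaches beyond the PACU. If a floor patient receives an opioid other than morphine, a literal reading of section 8.0 records less opioid than that patient received.

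Two consequences could follow. If the uncounted share is the same in both arms, the recorded values become noisier and the difference in mg shrinks, but the percentage reduction does not change. If the share differs by arm, the percentage reduction itself is distorted. Blinding does not rule this out, because a change of opioid can follow pain or side effects, and section 4.0 expects both to differ between arms.

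**Working it through.** **1. Where morphine is fixed and where it is not**

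| Setting | Opioid allowed | Opioid recorded |
|---|---|---|
| PACU (section 8.0) | IV morphine 2 mg, repeated | Amount of analgesic consumed |
| Floor (sections 8.0 and 9.0; form items 16 and 18.c) | Standard care, no drug named | Morphine at 24 hours |

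The PACU row is consistent. In the floor row, what may be given is wider than what is counted.

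**2. The plan's own figure**

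Section 11.0 states 32 per group, 80% power, 5% type 1 error and a 30% decrease. It gives no mean or SD, so 32 cannot be reproduced from the stated inputs. It can only be solved backwards, taking the test as two-sided (not stated) and using the normal approximation:

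- d = (1.960 + 0.842) × sqrt(2/32) = 0.700.
- With the SD proportional to the mean, d = 0.30 / (CV × sqrt((1 + 0.7²)/2)) = 0.30 / (0.863 × CV), so CV = 0.496.
- With a common SD instead, CV = 0.30 / 0.700 = 0.43. Both versions share d = 0.700. The first is used below.

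That this CV applies to 24-hour use is an assumption.

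**3. Equal use of other opioids in both arms**

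Let a share p of each arm receive another opioid and have only a fraction k of its use recorded as morphine. Neither p nor k is in the documents.

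- Recorded mean factor: m = (1 − p) + pk.
- Recorded CV = sqrt((1 + CV²) × ((1 − p) + pk²) − m²) / m.
- Power = Φ(d × sqrt(n/2) − 1.96), with d recomputed from the recorded CV.

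Example, p = 0.10 and k = 0.5: m = 0.95 and (1 − p) + pk² = 0.925. The recorded CV is 0.527 and d = 0.30 / (0.863 × 0.527) = 0.660. At n = 75, 0.660 × sqrt(37.5) − 1.96 = 2.08, so power is 98.1%.

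| p in each arm | k | Recorded CV | d | Power, 75 per arm | Power, 32 per arm |
|---|---|---|---|---|---|
| 0 | – | 0.496 | 0.700 | 99.0% | 80.0% |
| 10% | 0.5 | 0.527 | 0.660 | 98.1% | 75.2% |
| 25% | 0.5 | 0.568 | 0.612 | 96.3% | 68.7% |
| 10% | 0 | 0.620 | 0.560 | 92.9% | 61.1% |
| 25% | 0 | 0.813 | 0.427 | 74.4% | 40.1% |

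The 75 per arm is 150 split equally. The 32 per arm is the group size in section 11.0. The rows with k = 0 are extremes: over a window that includes the PACU, where rescue is morphine, such a patient would have needed no PACU morphine.

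In absolute terms, with assumed true means of 20 and 14 mg, p = 0.10 and k = 0.5, the recorded means are 20 × 0.95 = 19.0 and 14 × 0.95 = 13.3. The difference is 5.7 mg instead of 6.0 mg, and the ratio still shows a 30% reduction.

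**4. Unequal use by arm**

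Recorded reduction = 1 − 0.7 × m(ketamine) / m(control), for a true 30% reduction.

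| Control / ketamine share | k = 0.5 | k = 0 |
|---|---|---|
| 20% / 10% | 1 − 0.7 × 0.95/0.90 = 26.1% | 1 − 0.7 × 0.90/0.80 = 21.3% |
| 10% / 5% | 1 − 0.7 × 0.975/0.95 = 28.2% | 1 − 0.7 × 0.95/0.90 = 26.1% |
| 10% / 20% | 1 − 0.7 × 0.90/0.95 = 33.7% | 1 − 0.7 × 0.80/0.90 = 37.8% |

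The error runs either way, depending on which arm has more uncounted opioid.

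**The case against.** The strongest reply is that nothing in the documents shows the event happening. No section says that another opioid is given on the floor. Items 16 and 18.c are short entries on an ethics form, not ordering rules, and more types of surgery say nothing about which opioid is prescribed. The 24-hour data collection form named in item 16 decides what is recorded; it is not in the text and may already list every opioid. All of this stands, and it limits the point to the wording of the definition.

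A second reply is that the hypothesis in section 4.0 predicts less supplemental IV morphine, so counting morphine measures what was predicted. This explains the wording. It does not restrict floor prescribing, and section 11.0 frames the sample size on opioid requirements, which is broader.

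A reader might infer that the trial's main comparison is compromised. The documents do not support that. Section 11.0 gives no window for the sized outcome, sections 3.0 and 4.0 point at least as much to the PACU, and no 24-hour opioid variable appears in the test list. The power figures above therefore illustrate what a 24-hour comparison would lose; they are not losses in a stated analysis.

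A reader might also infer that the gap hides a real benefit, because control patients with more pain or nausea would be switched more often. That is possible, but no section describes switching, the rates are assumed, and the opposite imbalance would exaggerate the benefit.

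**Conclusion.** The point holds as a gap in the outcome definition: the 24-hour item names morphine, floor opioids are not limited to morphine, and nothing in the text counts or converts any other opioid. Its practical size is unknown, because the documents give neither an SD nor a rate of other opioid use. In the moderate equal-use cases at the current enrolment, the loss is about 1 to 3 percentage points of power. It becomes material only if many patients have all their floor opioid uncounted or if the uncounted share differs by arm. These sizes rest on a CV back-solved from 32 per group, a true 30% reduction lasting to 24 hours, and invented values of p and k. This is a worthwhile inexpensive improvement to a secondary measure, and it does not threaten the PACU comparison.

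**What to change.** In section 8.0, replace the 24-hour morphine item with total opioid by any route from PACU arrival to 24 hours, taken from the medication record and converted to IV morphine equivalents with one conversion table named in the protocol. In section 11.0, list it as a secondary 24-hour opioid variable. Keep PACU morphine in mg as a separate variable. Prescribing and randomisation need no change.

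The cost is a short amendment to two sections and a few more entries on the 24-hour form. The drawback is that conversion ratios are approximate, but that is likely a smaller error than counting another opioid as zero. If the form already captures all opioids, the amendment only brings the protocol text into line with it.
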